**11.3. Calculation of Modified Body Mass Index (mBMI)**

$$\text{mBMI} = (\text{serum albumin [g/dL]} / 10) \times \text{BMI}$$

$$\text{BMI} = \text{body weight [kg]} / (\text{body height [cm]} / 100)^2$$

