- i. Clinical laboratory test (serum albumin)
- j. Target disease
- k. Disease type of ATTR-CM (wild-type, variant, or unknown)
- l. Genotype of ATTR-CM (only for patients with variants)
- m. Severity of heart failure (NYHA Functional Classification)
- n. Presence/absence of liver impairment/renal impairment\*, (only for liver impairment) severity  
  
\*Liver impairment/renal impairment are not transient laboratory abnormalities but represent events that require clinical consideration and follow-up.
- o. Confirmation of complication [enter the names of chronic diseases including TTR-FAP (including allergy), diseases requiring treatment, diseases or disorders with sequelae, diseases that are cured after a certain post-treatment follow-up, and other diseases or syndromes which are considered problematic]

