8.2.2. Patient characteristics and history of treatment

8.2.2.1. Patient characteristics

For the safety analysis set and the efficacy analysis set, the following patient characteristics will be tabulated as described in Section 8.1:

- Target disease [ATTR-CM, others]
- Gender [male, female]

- Age (continuous variable)
- Age [<15 years, ≥15 to <65 years, ≥65 years]
- Inpatient/outpatient status at the first prescription [inpatient, outpatient]
- Body height (continuous variable)
- Body weight (continuous variable)
- BMI [<18.5, ≥18.5 to <25, ≥25]
- TTR genotype [wild-type, variant, unknown]
- NYHA functional classification [Class I, II, III, IV]
- mBMI (continuous variable, see Section 11.3 for the calculation method)
- Severity of liver impairment [mild, moderate, severe, unknown]
- Liver impairment [absent, present, unknown]
- Renal impairment [absent, present, unknown]
- Complication [absent, present]
- Usage experience of this drug (administered this drug for the first time, transferred from clinical trials, transition from the treatment of ATTR-PN, no information)
- Pregnancy status [absent, present]
- Concomitant drug therapy [absent, present]
- Concomitant non-drug therapy (device therapy) [absent, present]

For the safety analysis set, the number and proportion of the following patients will be tabulated by System Organ Class (SOC) and Preferred Term (PT):

- Breakdown of complications

For the safety analysis set, the number and proportion of patients for each of the following breakdowns will be tabulated:

- Breakdown of concomitant medications (Concomitant medications are defined as drugs used between the start date of administration of this drug and the date of discontinuation or end date of administration of this drug among those entered in the drug therapy section of the case report form.)
- Breakdown of concomitant non-drug therapies (device therapies) (Concomitant non-drug therapies are defined as non-drug therapies (device therapies) performed between the start date of administration of

this drug and the date of discontinuation or end date of administration of this drug among those entered in the non-drug therapy (device therapy) section of the case report form.)

- The classification of device therapies (pacemaker, implantable cardioverter defibrillator [ICD], cardiac synchronization therapy [CRTP], biventricular pacing implantable cardioverter defibrillator [CRTD], other) will be tabulated. Other breakdowns will be listed.

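### The mBMI formula in SAP 11.3 divides albumin labelled g/dL by 10, so its unit label and its operator are inconsistent and mBMI programmed as printed would be mis-scaled

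*SAP*

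**What the plan says.** SAP 11.3 gives two formulas. The first forms mBMI from "serum albumin [g/dL]} / 10" (the brace is formula markup), multiplied by BMI. The second computes BMI as weight in kg over the square of height, with height in cm divided by 100 to reach metres.

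SAP 8.2.2.1 includes the index among the characteristics tabulated for the safety and efficacy analysis sets and sends the reader back to that formula: "mBMI (continuous variable, see Section 11.3 for the calculation method". Under SAP 8.1.1 a continuous variable is summarised by number of patients, mean, SD, median, maximum and minimum.

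Albumin is collected at the start of administration. Protocol 8.3.1 lists it as "Clinical laboratory test (serum albumin"), with no unit. SAP 11.3 is the only place in the SAP that names albumin, and neither document gives another mBMI formula, a unit for mBMI or a reference value.

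**The concern.** The two divisors in SAP 11.3 look like unit conversions of the same kind. The one for height is right: cm divided by 100 gives metres. The one for albumin is not. A value in g/dL divided by 10 is in grams per centilitre, which is not a usual unit for albumin. A factor of 10 applied to a g/dL value makes sense as a conversion to g/L, and that conversion is a multiplication.

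What is at stake is one row of the characteristics tables. A programmer who follows SAP 8.2.2.1 has only this formula to work from, and the table would carry no unit to alert a reader. The approval conditions quoted in both documents ask for the background of treated patients to be understood, so baseline description is one of the things this survey must deliver. mBMI is also the only summary of albumin that the SAP specifies by name.

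**Working it through.** The documents give no numerical mBMI, so there is no stated figure to reproduce. The check is a unit check plus direct evaluation.

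**Inputs**
- From SAP 11.3: mBMI = (albumin in g/dL ÷ 10) × BMI, and BMI = weight in kg ÷ (height in cm ÷ 100)².
- Unit identity: 1 g/dL = 10 g/L.
- Assumed target unit: g/L, the usual definition of the index. The documents do not state it, so g/dL is carried as the alternative.
- Illustrative patient (assumed): albumin 4.0 g/dL, which is 40 g/L, and BMI 22.

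**If albumin is held in g/dL, as labelled**
- As printed: (4.0 ÷ 10) × 22 = 8.8
- Target g/L: (4.0 × 10) × 22 = 880. Ratio 880 ÷ 8.8 = 100
- Target g/dL: 4.0 × 22 = 88. Ratio 88 ÷ 8.8 = 10

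The ratios do not depend on the patient: 10 ÷ (1/10) = 100 and 1 ÷ (1/10) = 10.

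**If the label is wrong and albumin is held in g/L**
- As printed: (40 ÷ 10) × 22 = 88
- This matches the g/dL index (88) and is 10 times below the g/L index (880).

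| Albumin held in | Formula as printed | Shortfall if the index uses g/L | Shortfall if the index uses g/dL |
|---|---|---|---|
| g/dL (as labelled) | 8.8 | 100 times (880) | 10 times (88) |
| g/L (label wrong) | 88 | 10 times (880) | none (88) |

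The printed operator is right only in the last cell, and there the printed unit label is wrong. With a g/dL input it gives neither index.

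**Range.** Over assumed albumin of 2.5 to 5.0 g/dL and BMI of 20.0 to 27.68 (45 kg at 150 cm to 80 kg at 170 cm):
- As printed: 2.5 ÷ 10 × 20.0 = 5.0, up to 5.0 ÷ 10 × 27.68 = 13.84
- Index in g/L: 500 to 1384
- Index in g/dL: 50 to 138.4

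Across this range the printed formula puts mBMI at no more than half of BMI, in a table that categorises BMI at 18.5 and 25.

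**Where the value goes.** mBMI is not among the endpoints (SAP 6.1 and 6.2) or the subgroup factors (SAP 5.4). It is not a term in the biomarker model (SAP 8.2.4.2) or a stratification factor for survival (SAP 8.2.4.4). It is one of 19 characteristics listed in SAP 8.2.2.1.

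**The case against.** The strongest reply is that the documents show an inconsistency without saying which half of it is wrong. The target unit is not stated, the protocol records albumin without a unit, and dividing by 10 is a correct step if the input is in g/L. On that reading the bracketed unit is the slip, the index is about 88 for the example patient, and a factor of 100 does not arise. This stands as a limit on the size of the error. It does not rescue the formula, because on that reading too the printed text needs correcting.

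The second reply is that the effect is small. It would be a constant multiplier on one descriptive row, in a survey that SAP 4 calls non-confirmatory. Patient ranking and relative spread are unaffected, the summary statistics can be recovered exactly by rescaling, and height, weight and BMI are tabulated separately. This stands in full and settles the severity.

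A reader might also infer that every tabulated mBMI is already 100 times too small and that the tables must be rerun. The documents do not support that. They show no program, output or mBMI value, and the factor of 100 needs a g/L target, albumin held in g/dL and literal programming. Nor do they support a claim that the survey loses comparability with other tafamidis data: neither document plans such a comparison for mBMI or gives values to compare.

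**Conclusion.** The point holds as a minor error in the SAP. The unit label and the operator in SAP 11.3 cannot both be right for an index in a usual albumin unit, and nothing elsewhere in the documents corrects the formula.

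Its size depends on assumptions that the documents leave open. With albumin in g/dL and the formula programmed as printed, mBMI is 100 times too small if the index uses albumin in g/L (the usual definition, taken here as an assumption), and 10 times too small if it uses g/dL. The mean, SD, median, minimum and maximum would all carry that factor. It would be tempting to rank this as something that must be fixed before any result can be trusted, but no safety, effectiveness, subgroup or model result depends on mBMI.

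**What to change.** - In SAP 11.3 write mBMI = (serum albumin [g/dL] × 10) × BMI and state the unit as kg/m² × g/L. If the g/dL index was intended, say so and drop the factor of 10.
- Confirm the unit in which albumin is held in the database. This matters because multiplying a value already in g/L by 10 would overshoot: 40 × 10 × 22 = 8800 against 880.
- Confirm the operator used in the program. Rerun the mBMI rows only if it followed the printed formula.
- Show the unit beside mBMI in the characteristics tables.

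The cost is one operator and one unit statement in the SAP, and a check of one program line.
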